Subjects will undergo computerized dynamic posturography testing via apparatus manufactured by Neurocom, Inc. This device is clinically used for measurement of balance impairment. It measures body sway under varying visual and vestibular cues [3]. Motor control test (MCT) measuring body sway during small translations of the support surface will also be used.

Conclusion of study:

Subjects will stop taking rasagiline or placebo once their 8 week supply runs out.

Power analysis to determine the number of subjects

To estimate number of subjects needed for the posturography test, we performed a power analysis using the software G*power [4]. For inputs, data from the effect of dopamine depleter tetrabenazine on posturography in Huntington's disease was used [5].

The strategy composite score here during the tetrabenazine ON state was 79.2, during tetrabenazine OFF state it was 63.5. Averaged SD for these two outcomes was 11.5 and the total sample size was 10. These data were used to calculate the anticipated effect size. This input provided the Effect Size $f = 0.6826087$ (Table 1).

Input of the effect size value into the G*power with requested $\alpha=0.05$ and power $(1-\beta)=0.9$, weighing in the repeated measurements (before and after rasagiline) with very low correlation among repeated measures resulted in returned total sample size of 10 subjects Table 1 (please see the table of calculated inputs and outputs below). This total number will be randomized into 2 groups of subjects: rasagiline monotherapy and placebo study arm. Similarly, there will be 10 subjects in the study arm with rasagiline as an adjuvant therapy versus placebo.

F tests - ANOVA: Repeated measures, between factors

Analysis: A priori: Compute required sample size

Input:	Effect size f	=	0.6826087
	α err prob	=	0.05
	Power ($1-\beta$ err prob)	=	0.9
	Number of groups	=	2
	Repetitions	=	4
	Corr among rep measures	=	.1
Output:	Noncentrality parameter λ	=	14.337066
	Critical F	=	5.317655
	Numerator df	=	1.000000
	Denominator df	=	8.000000
	Total sample size	=	10
	Actual power	=	0.910691

Table 1. G*power software inputs and outputs for statistical power

General approach for statistical evaluation of the study data

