The output of the posturography testing are computer-calculated scores. Though these scores are discrete (do not represent a continuous variable), they still may fit the requirements of parametric statistical tests. Thus, we will first test the raw scores for normal distribution using a Kolmogorov-Smirnov test versus dataset with known Gaussian distribution. If the scores are normally distributed, we will determine whether data variance is approximately equal in all tested groups. If these conditions are met, we will continue data evaluation using repeated measures ANOVA with between factor of drug (levels: rasagiline, placebo) and within factor of treatment (levels: before, after). Level of significance will be preset to 0.05. Since no multiple comparisons are planned, there will be no adjustments of p.

If we do not find the Gaussian distribution of scores or if the variances among the groups are unequal (difference of one order of magnitude or more), we will calculate non-parametric statistics to determine differences. For this purpose we will use Wilcoxon Signed Rank test and evaluate separately rasagiline and placebo groups with p preset to 0.05.

Abbreviations

COMT: Catechol-O-Methyltransferase

HD: Huntington's disease

MCT: Motor control test

PD: Parkinson's disease

References:

1. Wood BH, Bilclough, Bowron A. Incidence and prediction of falls in Parkinson's disease: a prospective multidisciplinary study. *J Neurol Neurosurg Psychiatry* 2002;72:721-725
5. [name], Davidson, A., Ondo, W.G., and Cohen, H.S. Effect of tetrabenazine on computerized dynamic posturography in Huntington disease patients. *Parkinsonism and Related Disorders* 2012;18(7):896-8.

Declarations**Ethics Approval and Consent to Participate**

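### Analysing the pre-drug baseline as a 'before' outcome level, with no baseline covariate, costs precision at the plan's own correlation of 0.1: about 1.56 times the variance with 5 per arm and one post-treatment visit

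*Combined protocol and SAP*

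**What the plan says.** The section on the general approach for statistical evaluation, and the abstract, specify a "repeated measures ANOVA with between factor of drug (levels: rasagiline, placebo) and within factor of treatment (levels: before, after"). The posturography section places the first evaluation before the first tablet and later ones at 4 and 8 weeks, so 'before' is a pre-treatment baseline. No section names a baseline covariate or any other baseline adjustment.

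The plan does not say which ANOVA term tests the hypothesis, or whether 'after' means week 4, week 8 or both. On the test level it says "Level of significance will be preset to 0.05".

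The power section states its correlation assumption in words, "with very low correlation among repeated measures resulted in returned total sample size of 10 subjects", and Table 1 enters .1 on the line "Corr among rep measures". The effect size comes from a tetrabenazine study in Huntington's disease: "The strategy composite score here during the tetrabenazine ON state was 79.2, during tetrabenazine OFF state it was 63.5", and "Averaged SD for these two outcomes was 11.5 and the total sample size was 10".

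**The concern.** A baseline score cannot be affected by the drug. Making it one level of the outcome leaves two candidate drug terms. The interaction subtracts the whole baseline score from the later one. The main effect averages the untreated score in with the treated one. Subtraction removes between-subject variation only if the two scores are well correlated. When the correlation is very low, as the plan assumes, subtraction mostly adds the baseline's own noise.

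Using baseline as a covariate lets the data decide how much of it to remove. With 5 subjects per arm precision is scarce, and the choice costs nothing in data collection because baseline is already measured on everyone.

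**Working it through.** **Inputs.** From the power section and Table 1: difference 79.2 − 63.5 = 15.7; SD 11.5; correlation ρ = 0.1; two-sided α = 0.05; 10 subjects per comparison (5 v 5). Assumed here: equal SDs at all visits, the same ρ between every pair of visits, normal scores.

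**The plan's own figure.** f = 15.7 / (2 × 11.5) = 0.6826. λ = f² × N × m / [1 + (m − 1)ρ] = 0.46595 × 10 × 4 / 1.3 = 14.337. With critical F(1, 8) = 5.3177, power is 0.9107. Table 1 is reproduced. It is a between-factors test averaging 4 repetitions that all carry the full effect, so it is neither of the before/after drug terms below.

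**Variance per subject, one post-treatment visit, in units of SD².**
- Interaction (difference in change): 2(1 − ρ) = 1.80.
- Baseline as covariate: 1 − ρ² = 0.99 in large samples. Estimating the slope with N = 10 multiplies this by (N − 3)/(N − 4) = 7/6, giving 1.155.
- Main effect, rescaled because averaging in the untreated baseline halves the effect: 2(1 + ρ) = 2.20.
- Post-treatment score alone: 1.

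Interaction v covariate: 1.80 / 0.99 = 1.82 in large samples; 1.80 / 1.155 = 1.56 at 5 per arm (simulation agrees). Standard errors: 11.5 × √(1.80 × 2/5) = 9.8 points and 11.5 × √(1.155 × 2/5) = 7.8 points.

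**Variance, mean of weeks 4 and 8.** The mean has variance (1 + ρ)/2 = 0.55. Change: 0.55 + 1 − 0.2 = 1.35. Covariate: 0.55 − 0.01 = 0.54, times 7/6 = 0.63. Ratio 1.35 / 0.63 = 2.14 (2.15 simulated).

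**Power, one visit.** For change, main effect and post-only, the noncentrality is (N/4)d²/v, where d = 15.7/11.5 = 1.365 and v is the variance above, on 1 and 8 df. For the covariate model, power is simulated on 1 and 7 df. The variance ratio is (2 − 2ρ) / [(1 − ρ²) × 7/6].

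| ρ | Variance ratio, change v covariate | Change (interaction) | Baseline as covariate | Post-only | Main effect |
|---|---|---|---|---|---|
| 0.1 | 1.56 | 0.29 | 0.42 | 0.48 | 0.25 |
| 0.3 | 1.32 | 0.36 | 0.45 | 0.48 | 0.22 |
| 0.5 | 1.14 | 0.48 | 0.52 | 0.48 | 0.20 |
| 0.7 | 1.01 | 0.69 | 0.68 | 0.48 | 0.18 |
| 0.8 | 0.95 | 0.85 | 0.82 | 0.48 | 0.17 |

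**Power, two-visit mean.** Change v covariate is 0.37 v 0.66 at ρ = 0.1, and 0.59 v 0.69 at ρ = 0.5.

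**The case against.** The before/after interaction is a standard test and, under randomisation, unbiased. The loss is one of efficiency only, and its size rests on a planning entry of 0.1 for which the documents give no data. At a correlation of 0.7 there is nothing to gain with one visit, and at 0.8 the change score is slightly better. All of this stands, and it keeps the point at the level of an improvement.

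The covariate model is also not the best choice at the plan's own correlation. With 5 per arm, estimating a slope near zero costs more than it returns, so ignoring baseline does slightly better: 0.48 v 0.42 at ρ = 0.1, and 0.48 v 0.45 at 0.3. That stands too. The case for the covariate is that the true correlation is unknown. Post-only stays at 0.48 whatever ρ is, the change score is poor when ρ is low, and the covariate model is never far from the better of the two.

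Three stronger readings are tempting but unsupported:
- **That the planned model nearly doubles the variance.** The one-visit ratio of 1.82 is the large-sample value; at 5 per arm it is 1.56.
- **That chance baseline imbalance is a serious threat here.** Its SD is 11.5 × √(2/5) = 7.3 points, but at ρ = 0.1 only about 0.1 × 7.3 = 0.7 points carries into the outcome, about 5% of 15.7.
- **That adjustment would rescue the sample size.** At ρ = 0.1 it gives 0.42, or 0.66 with two visits, against a stated 0.90.

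**Conclusion.** The concern holds as a loss of precision. If the interaction is the test and the plan's correlation of 0.1 is right, the planned analysis carries about 1.56 times the variance of a baseline-adjusted comparison with one post-treatment visit, and about 2.15 times with the mean of weeks 4 and 8. If the main effect is meant, the one-visit loss is larger and power falls further as the correlation rises.

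The conclusion rests on equal SDs, a common correlation and the plan's own 15.7-point difference. It is conditional on a term and a visit that the plan leaves unnamed. The one-visit advantage over the interaction is substantial only at low correlation. The point concerns the parametric branch only.

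**What to change.** In the statistical evaluation section and in the abstract, replace the before/after ANOVA with a linear model of the post-treatment score on drug, with the subject's baseline score as covariate. If both post-treatment visits are used, take their mean as the outcome. Report the adjusted rasagiline-minus-placebo difference with its 95% interval.

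The cost is wording. The declarations state that no patients were enrolled, so the change can be made before any data exist. The statistical price is:
- one residual degree of freedom (7 instead of 8);
- an assumed linear baseline slope;
- slightly lower power than the change score at a correlation of about 0.8 or above;
- slightly lower power than a post-only comparison at about 0.1 to 0.3.

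The gap to 0.90 power needs separate treatment.

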Effect of rasagiline on balance in Parkinson's disease as measured by computerized posturography

[name]

Approved: 9/15/2014

Department of Neurology

New York Medical College, Valhalla, NY

United States of America

Corresponding Author

[name]

[name]

[name]

United States of America

[contact]

[contact]

Email: [contact]

Keywords: rasagiline, balance, posturography, Parkinson's disease

Abstract:**Background:**

Falls occur in a majority of Parkinson's disease (PD) patients. Balance disturbance can be measured by computer dynamic posturography. The effect of monoamine oxidase inhibition on PD patients as measured by computer dynamic posturography has not been previously studies.

Methods:

The study will test the hypothesis that therapy with rasagiline improves balance in PD patients as measured by computerized dynamic posturography. 5 subjects will be randomized to rasagiline or placebo and 5 further subjects will be randomized to rasagiline as adjuvant therapy versus placebo. Subjects will be analyzed by computerized dynamic posturography testing. The device measures body sway under varying visual and vestibular cues and is used for assessment of balance. Subjects will be evaluated at baseline prior to taking first tablet as well as at 4 weeks and 8 weeks. In the adjuvant therapy arm, subjects will be evaluated on rasagiline but in a functional OFF state for their other PD medications. If the scores are normally distributed, we will determine whether data variance is approximately equal in all tested groups. If these conditions are met, data evaluation will continue using repeated measures ANOVA with between factor of drug (levels: rasagiline, placebo) and within factor of treatment (levels: before, after). Level of significance will be preset to 0.05.

Background:

Posturography testing for Parkinson's disease patients on monoamine oxidase (MAO) inhibitors in general has not been studied previously. In Wood's study of patients with Parkinson's disease, falls occurred in 68.3% of the subjects [1]. In Ebmeier's population study of idiopathic Parkinson's disease patients, signs of postural instability on clinical examination were among the factors listed in premature death [2].

Hypothesis

The hypothesis is that therapy with rasagiline improves balance in PD patients as measured by computerized dynamic posturography.

Methods:**Inclusion Criteria:**

1. 18 years old or above

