2. Clinical diagnosis of Parkinson disease by verified by movement disorders expert at the initial study visit with at least two cardinal signs of the disease (rest tremor, bradykinesia, rigidity, and postural instability).
3. For the monotherapy arm, patients must not be on amantadine, dopamine agonists, or levodopa. For the adjuvant therapy arm: Patients must be on a stable dose of their current medication for treatment of Parkinson disease which may include any combination of the following: amantadine, trihexiphenydil, dopamine agonist, and/or levodopa.
4. Patients may continue their stable dose of tricyclic, selective serotonin reuptake inhibitor, or serotonin norepinephrine reuptake inhibitor if they are on these medications at randomization.

Exclusion Criteria:

1. Catechol-O-Methyltransferase (COMT) inhibitor therapy use 30 days prior to start of study (both study arms).
2. Dopamine receptor blocker use (such as quetiapine) one week prior to taking study drug
3. For both monotherapy and adjuvant therapy arms: use of MAO inhibitor therapy including selegiline or rasagiline within 30 days prior to taking study drug and first posturography evaluation.

Study Visits:**Screening:**

Patients will be evaluated by movement disorders expert who will confirm diagnosis of Parkinson disease as stipulated in inclusion criteria. Blood pressure and heart rate, as well as a complete Unified Parkinson Disease Rating Scale (UPDRS) evaluation will be performed.

Randomization:

Subjects will be randomized by facility pharmacy to either placebo or rasagiline 1 mg daily for 8 weeks. There will be 5 rasagiline monotherapy and 5 matching placebo subjects as well as 5 rasagiline adjuvant therapy and 5 matching placebo subjects.

Computerized dynamic posturography evaluation:

Subjects will be evaluated at baseline prior to taking first tablet as well as at 4 weeks and 8 weeks. In the adjuvant therapy arm, subjects will be evaluated on rasagiline but in a functional OFF state for their other PD medications.

Functional OFF will be defined as at least 24 hours post last dose of long acting dopamine agonist or levodopa extended or continuous release formulations, at least 8 hours post last dose of immediate release dopamine agonist, immediate release levodopa, or trihexyphenidyl.

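### The plan does not name the F test that answers the hypothesis, and Table 1 powers the drug main effect as if the full difference were present at all four repetitions, so the stated power of 0.91 does not apply to the planned analysis

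*Combined protocol and SAP*

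**What the plan says.** The Hypothesis section reads: "The hypothesis is that therapy with rasagiline improves balance in PD patients as measured by computerized dynamic posturography". The section on the general approach to statistical evaluation proposes, if normality and variance checks pass, a "repeated measures ANOVA with between factor of drug (levels: rasagiline, placebo) and within factor of treatment (levels: before, after" model at a 0.05 level with no adjustment of p. It does not say which of the resulting F tests is the test of the hypothesis. The word interaction does not appear in the document.

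Table 1, in the power analysis section, is labelled "F tests - ANOVA: Repeated measures, between factors". It has 2 groups, 4 repetitions, correlation 0.1, effect size f = 0.6826087, degrees of freedom 1 and 8, total sample size 10 and power 0.910691. The effect size comes from a tetrabenazine study in Huntington's disease: "The strategy composite score here during the tetrabenazine ON state was 79.2, during tetrabenazine OFF state it was 63.5", and "Averaged SD for these two outcomes was 11.5 and the total sample size was 10".

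The posturography section gives three assessments: "Subjects will be evaluated at baseline prior to taking first tablet as well as at 4 weeks and 8 weeks". The Randomization section gives 5 rasagiline and 5 placebo subjects in each of the monotherapy and adjuvant strata.

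**The concern.** A two-by-two mixed ANOVA yields three tests, and they answer different questions.

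- **Drug main effect.** It compares the arms on each subject's average of a pre-drug and a post-drug score. Randomised arms have no expected difference before the first tablet, so the expected contrast is half the true post-treatment difference. The test remains valid under the null, but it estimates a diluted effect.
- **Treatment main effect.** It compares before with after across both arms, and so mixes drug effect with placebo response and practice on the platform.
- **Drug-by-treatment interaction.** It compares the change on rasagiline with the change on placebo, which is what the hypothesis concerns.

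With no test named and p unadjusted, any of the three could be read at 0.05, including a before/after change shared with placebo. Separately, the one test that the document does identify, through Table 1, is the drug main effect, and it is powered on an undiluted difference at more repetitions than the analysis has. The sample size therefore rests on a power figure that does not belong to the planned analysis.

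**Working it through.** **Inputs.** From the power analysis section: means 79.2 and 63.5 (difference δ = 15.7), SD 11.5, ρ = 0.1, α = 0.05. From the Randomization section: 5 v 5 per stratum, N = 10. I assume compound symmetry, equal SDs, no expected baseline difference, no placebo change and no dropout. Correlations other than 0.1 are my assumptions.

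**1. Reproduce Table 1.** f = (15.7/2)/11.5 = 7.85/11.5 = 0.6826, so f² = 0.46595. For the between-factor test with m repetitions, λ = f²·N·m / [1 + (m−1)ρ].

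With m = 4: λ = 0.46595 × 40 / 1.3 = 14.337. The critical F(1, 8) is 5.3177 and power is 0.9107. This matches Table 1 exactly, so the table is the drug main effect with the full difference at every repetition.

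**2. Use the two levels of the planned ANOVA, still undiluted.** λ = 0.46595 × 20 / 1.1 = 8.472; power 0.72.

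**3. Allow for no difference at baseline.** The contrast is 15.7/2 = 7.85, so f becomes 0.3413 and λ = 8.472/4 = 2.118; power 0.25. At ρ = 0.5 and 0.8 it is 0.20 and 0.17.

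**4. Other layouts of the drug main effect, ρ = 0.1.**
- Three visits, full effect at weeks 4 and 8: the factor is 2/3, λ = 0.46595 × (4/9) × 30 / 1.2 = 5.177; power 0.52.
- Four repetitions, one untreated: the factor is 3/4, λ = 14.337 × 9/16 = 8.065; power 0.70. The document does not say what the four repetitions are.

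**5. Drug-by-treatment interaction.** In the two-level layout this equals a two-sample t test on change scores: λ = N·δ² / [8·SD²·(1−ρ)], df 1 and N−2.

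At ρ = 0.1: λ = 10 × 246.49 / (8 × 132.25 × 0.9) = 2464.9/952.2 = 2.589; power 0.29. For 90% power, N = 42 gives 0.896 and N = 44 (λ = 11.390, df 1 and 42) gives 0.91, so about 44 per stratum are needed.

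Simulation with 20,000 runs at ρ = 0.1 gave 0.25 for the two-level drug main effect and 0.29 for the interaction.

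**6. ANCOVA of the post-treatment score on baseline.** The residual variance is SD²(1−ρ²), with 7 error df. The simple formula λ = δ² / [SD²(1−ρ²) × 0.4] ignores chance baseline imbalance, which matters at 5 v 5, and gives power that is 4 to 5 points too high. Allowing for the imbalance replaces 0.4 by 0.4 + D²/W, where D is the baseline difference between arms and W the pooled within-arm baseline sum of squares. The ANCOVA row below averages over that imbalance.

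| Test, N = 10 | ρ = 0.1 (plan) | ρ = 0.5 (assumed) | ρ = 0.8 (assumed) |
|---|---|---|---|
| Table 1 as stated | 0.91 | – | – |
| Drug main effect, before/after | 0.25 | 0.20 | 0.17 |
| Drug main effect, three visits | 0.52 | 0.34 | 0.28 |
| Interaction, before/after | 0.29 | 0.48 | 0.85 |
| ANCOVA on baseline | about 0.42 to 0.43 | about 0.52 | about 0.82 |

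**The case against.** Software prints the interaction from this model by default. A drug factor crossed with a before/after factor, next to a hypothesis that the drug improves balance, is compatible with an intention to read it. That stands: a reader might infer that the plan commits to the drug main effect as its test, and the text does not say so. What it does is leave the choice open. The non-parametric fallback does not settle the matter either, since it analyses the rasagiline and placebo groups separately and has no comparison between arms.

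A reader might also infer that Table 1 itself halves the effect. It does not. It enters the full f, and the dilution arises when a drug main effect is computed on data that include the baseline. Nor is the whole fall from 0.91 to 0.25 due to the untreated baseline. Moving from 4 repetitions to 2 already takes power to 0.72, and dilution does the rest. The halving is exact only for the two-level layout.

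Finally, power is not the reason to prefer the interaction. At ρ = 0.1 it has 0.29 against 0.25 for the two-level main effect, and the three-visit main effect (0.52) exceeds it. The larger powers appear only at correlations that the document does not give. The reason to name the interaction or ANCOVA is that each targets the full drug effect.

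**Conclusion.** The point holds as a gap in pre-specification together with a power calculation that does not match the analysis. No F test is tied to the hypothesis, and Table 1's 0.91 is the power of a drug main effect with 15.7 points at all four repetitions, which neither the visit schedule nor the ANOVA provides. At the plan's own inputs the power is 0.25 for the two-level main effect and 0.29 for the interaction.

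Naming the interaction does not rescue a sample of 10 per stratum at ρ = 0.1. The low correlation that raises the power of Table 1's test lowers that of the interaction, so the choice of test changes the sample size. If the true correlation were near 0.8, the interaction would have 0.85, but the document offers no support for that value. The three-visit figures also need the full effect to be present by week 4. The Declarations report that no data were gathered, so no result is affected and the text can be corrected before any use.

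**What to change.** In the statistical evaluation section, name one primary test: either the drug-by-treatment interaction or an ANCOVA of the post-treatment score with baseline as covariate. Choose one, because they target the same effect but are different tests with different power. State which visit (week 4 or week 8) is *after*. State that the drug and treatment main effects will not be used as tests of the hypothesis.

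Then rerun Table 1 for the chosen test, with the actual number of assessments and a justified correlation, preferably over a range, and restate the power or the sample size.

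The work is a few sentences and one new power run. ANCOVA spends one of the 8 error degrees of freedom. The real cost is that the trial must either acknowledge much lower power at 10 per stratum or plan for more subjects, about 44 per stratum for 90% power on the interaction at ρ = 0.1.

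### Three posturography visits feed a two-level before/after ANOVA that does not say which visit is 'after' and has no rule for a missing week-8 score

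*Combined protocol and SAP*

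**What the plan says.** The section on computerized dynamic posturography evaluation sets three test occasions: "Subjects will be evaluated at baseline prior to taking first tablet as well as at 4 weeks and 8 weeks". The section on the general approach to statistical evaluation, and the abstract, plan a repeated measures ANOVA with drug as the between-subject factor and a "within factor of treatment (levels: before, after" factor within subjects. If normality or equal variance fails, the fallback is a Wilcoxon signed rank test within each group, which also needs a pair of scores per subject.

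The power section takes the G*Power total of 10 as the number to randomise: "This total number will be randomized into 2 groups of subjects: rasagiline monotherapy and placebo study arm". The adjuvant cohort has the same size, and the randomisation section gives 5 per arm in each cohort. Table 1 is headed "F tests - ANOVA: Repeated measures, between factors" and uses 4 repetitions with a correlation of 0.1.

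The document does not map the three visits to the two levels. It says nothing about missed visits, early stopping, replacement of subjects or the analysis population.

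**The concern.** Three visits cannot enter a two-level factor without a choice, and the plan leaves that choice open. It matters in two ways.

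First, one on-treatment visit is either unused or used at the analyst's discretion. If the choice is made after the scores are seen, week 4, week 8 or their mean could each be reported as the planned analysis.

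Second, a conventional repeated measures ANOVA needs a complete set of levels from each subject. If 'after' is week 8, or if both visits are required, a subject without week 8 leaves the analysis. The comparison then covers completers only, and it is open to bias if stopping is related to treatment or to balance. Filling in week 4 for those subjects alone would mix 4-week and 8-week exposure under one label. With 5 subjects per arm, a single case weighs heavily, and the number randomised includes no allowance for loss.

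**Working it through.** **1. What happens to a subject with baseline and week 4 but no week 8**

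| Meaning of 'after' | Subject in the two-level ANOVA? |
|---|---|
| Week 8 | No |
| Both visits required | No |
| Week 4 for everyone | Yes, but week 8 is unused for all |
| Mean of available on-treatment scores | Yes, with shorter exposure than the others |
| Week 8, with week 4 substituted if missing | Yes, with exposure differing between subjects |

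The plan selects none of these rows. One subject lost from an arm is 1/5 = 20%.

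**2. Reproducing Table 1**

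Inputs from the power section: means 79.2 and 63.5, SD 11.5, alpha 0.05, m = 4 repetitions, correlation ρ = 0.1, N = 10 in two groups.

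- f = (79.2 − 63.5)/(2 × 11.5) = 15.7/23 = 0.6826
- λ = f² × m/(1 + (m − 1)ρ) × 4n₁n₂/N, with 1 and N − 2 degrees of freedom
- At 5 v 5: λ = 0.46595 × 4/1.3 × 10 = 14.337, critical F = 5.318, power = 0.911

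This matches the stated λ of 14.337066 and power of 0.910691.

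**3. The same formula with the number of repetitions varied**

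For 5 v 4, 4n₁n₂/N = 80/9 = 8.889 and the critical F is 5.591.

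| Repetitions m | λ, 5 v 5 | Power, 5 v 5 | λ, 5 v 4 | Power, 5 v 4 |
|---|---|---|---|---|
| 4 (Table 1) | 14.337 | 0.911 | 12.744 | 0.863 |
| 3 (scheduled visits) | 11.649 | 0.847 | 10.355 | 0.788 |
| 2 (before, after) | 8.472 | 0.723 | 7.531 | 0.655 |

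**4. The contrast that a before/after comparison of drugs rests on**

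Table 1 powers the drug main effect, not drug by time. As an illustration only, assume that the 15.7 points are a difference in change and that the SD is 11.5 at each visit. The SD of change is 11.5 × √(2(1 − ρ)), and the noncentrality of the t test is 15.7/(SD of change × √(1/n₁ + 1/n₂)).

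| Assumed ρ | Noncentrality, 5 v 5 | Power, 5 v 5 | Power, 5 v 4 |
|---|---|---|---|
| 0.1 | 1.61 | 0.29 | 0.26 |
| 0.5 | 2.16 | 0.48 | 0.42 |
| 0.7 | 2.79 | 0.69 | 0.62 |

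**5. What a three-visit model recovers**

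Take compound symmetry with known correlation, 5 complete subjects in one arm, and 4 complete plus one without week 8 in the other. Let V be the 3 × 3 correlation matrix and V₂ its baseline/week-4 block. The information in the second arm is 4V⁻¹, with V₂⁻¹ added to the baseline/week-4 block. The variance of the drug difference in change to week 8, in units of SD², is then:

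| Assumed ρ | Subject dropped: 2(1 − ρ)(1/5 + 1/4) | Subject kept | Reduction |
|---|---|---|---|
| 0.1 | 0.810 | 0.769 | 5.0% |
| 0.5 | 0.450 | 0.433 | 3.7% |
| 0.7 | 0.270 | 0.261 | 3.3% |

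For the difference in average on-treatment change, the same calculation gives 0.6075 against 0.5523 at ρ = 0.1 (9.1%) and 0.2025 against 0.1853 at ρ = 0.7 (8.5%).

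**The case against.** The strongest reply is that the plan never ties 'after' to week 8. A subject who stops tablets between weeks 4 and 8 already has a baseline and a week-4 score, and stopping tablets need not mean missing the week-8 test. Under some readings, nobody is lost. This stands. A reader might infer that the ANOVA cannot use such a subject, but the documents do not support that; the loss is conditional on a definition they do not give.

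A reader might also infer that 0.91 is the power if all 10 complete, and that one early stopper is what takes it below 0.90. On Table 1's own inputs, one loss does give 0.863. But those inputs use 4 repetitions and a between-factors test. With the two levels actually planned, the figure is 0.723 with no loss at all. Labelling 0.91 as the full-completion power would endorse a figure that the planned analysis does not reach.

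Finally, it can be said that a mixed model is partly a preference and that defining 'after' with a missing-score rule would close the gap. That is fair as to the minimum. The model recovers little precision for a week-8 contrast. Its stronger justification is that it uses every scheduled visit and keeps every randomised subject who has data, without a substitution rule.

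**Conclusion.** The point holds as a gap in specification: 'after' is undefined, and no rule covers a missing week-8 score. The consequence is conditional. If week 8 or both on-treatment visits are needed, each subject without week 8 removes 20% of an arm although a week-4 score exists. How often this would happen cannot be sized, because the documents give no withdrawal rate.

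The stated 0.91 is arithmetically right for its inputs but does not describe the two-level analysis. The alternative powers in the repetition table assume that f = 0.6826 and ρ = 0.1 still apply. The drug-by-time powers further assume that the 15.7-point difference carries over to change scores, and are illustrative. This is a change that should be made; it does not by itself invalidate the design.

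**What to change.** 1. State that every randomised subject is asked for the week-4 and week-8 posturography, whether or not still taking tablets, and is analysed in the group assigned.
2. Replace the two-level ANOVA with a mixed model for repeated measures: drug, visit (baseline, 4 and 8 weeks) and drug × visit, with compound-symmetry covariance and Kenward-Roger degrees of freedom. A subject without week 8 then contributes baseline and week 4.
3. Name one drug-by-visit contrast in advance as primary, for example the difference between drugs in change to week 8.
4. Define in the same terms which scores the non-parametric fallback pairs, and what it does with a missing score.
5. Restate power for that model and contrast, with no loss and with one loss per cohort. Do not carry over 0.91.

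The cost is analysis wording and a less favourable power statement. No visits are added to the schedule. The model assumes that data are missing at random given the observed scores, and the precision gained per incomplete subject is modest. The declarations state that no patients were enrolled and no data gathered, so the change can be made before any start or reuse of the design.
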